7. PLANNED ANALYSIS

For End-Of-Text tables, the set of summary statistics is: N / Mean / SD / Min / Median / Max.

For tables that are provided for endpoints with some extreme data, median, quartiles and percentiles should be preferred to mean, standard deviation, minimum and maximum

Tabulations of frequencies for categorical data will include all possible categories and will display the number of observations in a category as well as the percentage (%) relative to the respective treatment group (unless otherwise specified, all patients in the respective patient set whether they have non-missing values or not). Percentages will be rounded to one decimal place. The category missing will be displayed only if there are actually missing values.

7.1 DEMOGRAPHIC AND OTHER BASELINE CHARACTERISTICS

Only descriptive statistics are planned for this section of the report.

For baseline eGFR calculations (MDRD) the following rules are to be applied regarding multiple race categories and Japanese patients:

- eGFR for patients with multiple race category Black & White will be calculated as eGFR for patients with race category Black
- eGFR for patients with multiple race category American Indian/Alaska Native & White will be calculated as eGFR for patients with race category White
- eGFR for patients with race Asian outside the region Asian will be calculated as eGFR for Japanese patients.

7.2 CONCOMITANT DISEASES AND MEDICATION

Only descriptive statistics are planned for this section of the report. Concomitant medication table will additionally be produced at Week 52 for Japanese patients only.

7.3 TREATMENT COMPLIANCE

Compliance with trial medication intake will be calculated by the investigator as a percentage of the number of pills taken relative to the number of pills that were planned to be taken since the last visit. On the eCRF only the information whether this calculated compliance was within the range of 80% to 120% since the previous visit is recorded. Treatment interruptions of greater than 7 consecutive days will be recorded in the eCRF.

Only descriptive statistics are planned for this section of the report.

7.4 PRIMARY ENDPOINT

7.4.1 Primary efficacy analysis

The primary analysis will be performed on the FAS (OC); patients will be assigned to the treatment they were randomised to and analysed according to the stratum to which they belong (regardless of any incorrect assignment to treatment based on identification of wrong stratum).

Mean changes from baseline in HbA_{1c} after 24 weeks of treatments will be analysed using a restricted maximum likelihood-based repeated measures approach (mixed model repeated measures [MMRM]).

Analyses will include the fixed, categorical effects of *treatment*, *week*, and *treatment by week* interaction – accounting for the respective sources of variation. The model also includes the continuous, fixed linear covariates of *baseline HbA_{1c}*, *baseline daily basal insulin dose* and *baseline HbA_{1c} by week interaction* that control the *treatment* and *week* effects for possible impact from these underlying factors. An unstructured (co)variance structure will be used to model the within patient measurements.

If this analysis fails to converge, the following covariance structures will be tested: Toeplitz, AR (1), and compound symmetry. The (co)variance structure converging to the best fit, as determined by Akaike's information criterion, will be used as the primary analysis.

The Kenward-Roger approximation will be used to estimate denominator degrees of freedom. Significance tests will be based on least-squares means using a two-sided $\alpha = 0.05$ [two-sided 95% confidence intervals (CI)]. The residuals are assumed to have a multivariate normal distribution with zero means and covariance matrix as specified above. All analyses will be implemented using SAS[®]. The primary treatment comparisons will be the contrast between treatments at Week 24.

The statistical model will be:

$$\begin{aligned} \text{HbA}_{1c} \text{ change from baseline} &= \text{overall mean} + \text{treatment} + \text{week} \\ &+ \text{treatment by week interaction} \\ &+ \text{baseline HbA}_{1c} + \text{baseline daily basal insulin dose} \\ &+ \text{baseline HbA}_{1c} \text{ by week interaction} \\ &+ \text{random error.} \end{aligned}$$

The model's random error is assumed to follow a normal distribution.

For Week 24 analysis, all levels for factor *week* up to Week 24 are to be considered in the model, [REDACTED]

In addition, descriptive statistics for HbA_{1c} (in %) over time are presented for FAS(OC), FAS(OC-ROC) and FAS(LOCF).

[REDACTED]

[REDACTED]

[REDACTED]

[REDACTED]

[REDACTED]

[REDACTED]

[REDACTED]

[REDACTED]

[REDACTED]

[REDACTED]

[REDACTED]

[REDACTED]

[REDACTED]

[REDACTED]

[REDACTED]

- [REDACTED]

[REDACTED]

[REDACTED]

- [REDACTED]

- [REDACTED]

- [REDACTED]

[REDACTED]

[REDACTED]

- [REDACTED]

- [REDACTED]

[REDACTED]

[REDACTED]

[REDACTED]

[REDACTED]

[REDACTED]

[REDACTED]

[REDACTED]

[REDACTED]

[REDACTED]

[REDACTED]

[REDACTED]

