##### Discontinuing or withdrawing patients from the trial

If a patient discontinues (drops out or withdraws) from this trial after randomization, the patient will not be replaced.

Patients have the right to withdraw from this trial at any time for any reason. The patients will be asked by the investigator to provide the specific reason for their withdrawal from the trial (e.g., moving out of the state or country, unable to drive to trial site, etc.) and this reason will be recorded on the eCRF.

Patients who discontinue from this trial are not allowed to re-enrol in this trial, including patients from other trial sites.

Patients will be discontinued from the trial for:

- significant non-compliance (If the patient fails to comply with the protocol (e.g., non-compliance with study medication or evaluations), a patient may be discontinued after discussion between investigator and sponsor),
- concomitant drugs that interfere with the medications being given in this trial,
- no longer being able to participate for other medical reasons (e.g., surgery, AEs, or other diseases),
- persistent hyperglycaemia that is uncontrolled with rescue medication as described in [Section 4.2.1](#) (In this case, the reason for discontinuation will be classified as “lack of efficacy”), and
- occurrence of hypoglycaemia that may put the patient at risk with continued participation (e.g., repeated hypoglycaemic episodes).
- If pancreatitis is suspected, the study medication should be stopped.

The investigator also has the right to withdraw patients from the trial because continuation of study medication or continuation of the follow up visits may not be in the best interest of the patient.

If necessary for patient safety, as determined by investigator, new antidiabetic medication regimen may be started the day after study medication discontinuation. The new antidiabetic medication must be recorded in eCRFs.

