### Treatment Period (Visits 3, 4, 5, 6, 98)

Visits should be performed fasting and as indicated in the [Flow Chart](#), and [Table 4.1.4: 1](#) and the respective protocol sections.

For Visit 98, patients will be entered in IRT as completing or discontinuing treatment.

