#### 7.5 RANDOMISATION

The sponsor will arrange for the randomisation as well as packaging and labelling of study medication. Eligible patients will be randomly assigned to one of the two treatment groups, with equal allocation of treatments. The randomisation list will be generated using a validated system, which involves a pseudo-random number generator so that the resulting treatment sequence will be both reproducible and non-predictable.

The randomisation will be stratified by HbA1c (< 8.5% vs. ≥ 8.5%) as determined from the blood sample taken at Visit 1 and insulin dose (< 40 international units total daily dose vs. ≥ 40 international units total daily dose) as determined at the beginning of the placebo run-in period (Visit 2). To ensure appropriate representation of patients with insulin doses of < 40 international units total daily dose as well as ≥ 40 international units total daily dose, the trial team will monitor the proportion of patients being recruited into these categories. The limitation of recruitment of a particular category may be arranged (on trial level and/or country level).

The allocation process will be performed at Visit 3 through IRT. However, the IRT allocation and randomization will not increase the study medication bottles at each trial site based on stratification.

Access to the code will be restricted to dedicated randomisation personnel and any exceptional access to the code (in case of an emergency) will be documented according to the sponsor's SOPs.

The trial will only be unblinded after all eCRF and electronic data have been entered into the trial database, after queries have been resolved, and after the database has been locked. Access to the codes will be controlled and documented by a signed confidentiality statement, which will be stored in the TMF.

Practical aspects of the treatment allocation process and methods to carry out blinding are detailed in [Sections 4.1.2](#) and [4.1.5](#), respectively.

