**A total of 300 patients will be randomised.**

Proprietary confidential information.

© 2015 Boehringer Ingelheim International GmbH or one or more of its affiliated companies. All rights reserved.

This document may not - in full or in part - be passed on, reproduced, published or otherwise used without prior written permission.

Based on pooled data from the 1218.36 and 1218.63 trials [REDACTED] assuming a standard deviation of 1.2% in both groups in the FAS with a 0.77% difference in HbA1c change from baseline in treatments, a number of 150 patients in each treatment arm will show superiority with a power >99%. This determination of power is based on a Student's t-test and a two-sided significance level of 5%.

Software package nQuery version 7.0 was used to derive the sample size.

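### If the unstructured model fails to converge, the primary analysis falls back only to equal-variance covariance structures, so the Week 24 standard error is wrong whenever the Week 24 variance differs from the average over visits

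*SAP*

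**What the plan says.** The primary analysis (SAP 7.4.1, and in the same terms Protocol 7.3.1) is a restricted maximum likelihood repeated-measures model for change from baseline in HbA1c. The primary result is the treatment contrast at Week 24. The within-patient covariance is unstructured at first. If that model does not converge, "the following covariance structures will be tested: Toeplitz, AR (1), and compound symmetry"; the candidate with the best Akaike value then becomes the primary analysis. Degrees of freedom are by Kenward-Roger.

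The readable text lists no heterogeneous version of these structures and no empirical (sandwich) standard error. SAP 7.5.2 analyses FPG by the strategy used for the primary endpoint. It repeats the unstructured choice but not the fallback, so FPG presumably inherits it.

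The only information on spread is in the sample size section (Protocol 7.6), "assuming a standard deviation of 1.2% in both groups in the FAS". It is a single figure for the change after 24 weeks. No SD is given for Weeks 6, 12 or 18.

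**The concern.** As named, Toeplitz, AR(1) and compound symmetry differ in how they model correlation but share one restriction: the same residual variance at every visit. Under that restriction the Week 24 contrast takes its standard error from a variance averaged over Weeks 6 to 24. If the true Week 24 residual variance is above that average, the standard error is too small; if below, it is too large.

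Neither safeguard in the plan helps. Akaike's criterion chooses only among candidates with the same restriction. Kenward-Roger corrects for small-sample uncertainty in the estimated covariance, not for a wrong form of it. A prespecified fallback is there to protect the primary test when the first model fails, and this one can leave its confidence interval too narrow or too wide.

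**Working it through.** **Inputs from the documents.** SD 1.2%, difference 0.77%, 150 per arm, two-sided 5% (Protocol 7.6); equal allocation (Protocol 7.5); four post-baseline HbA1c visits, Weeks 6, 12, 18 and 24 (Protocol flow chart). **Assumed:** the SDs before Week 24, the correlations and the dropout, none of which the documents give.

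**1. The plan's own figure.** True standard error = 1.2 × √(2/150) = 0.1386. Then 0.77/0.1386 = 5.56, and power ≈ Φ(5.56 − 1.96) = Φ(3.60) = 0.9998. This agrees with the stated power above 99%.

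**2. Closed form, complete data.** With a separate mean for each visit and arm, and one common variance, the model-based Week 24 standard error is s × √(2/n), where s² is the mean of the four visit variances. This is exact for compound symmetry and very close for the other two. The ratio to the true standard error is s/SD(Week 24), and type I error = 2 × [1 − Φ(1.96 × ratio)].

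| Assumed SD at Weeks 6/12/18/24 | Mean variance | s | Ratio | Type I error |
|---|---|---|---|---|
| 1.1/1.15/1.2/1.2 | 1.353 | 1.163 | 0.969 | 5.7% |
| 1.0/1.1/1.15/1.2 | 1.243 | 1.115 | 0.929 | 6.9% |
| 0.9/1.05/1.15/1.2 | 1.169 | 1.081 | 0.901 | 7.7% |
| 0.7/0.95/1.1/1.2 | 1.011 | 1.005 | 0.838 | 10.1% |
| 1.2 throughout | 1.440 | 1.200 | 1.000 | 5.0% |
| 1.2/1.1/1.0/0.9 | 1.115 | 1.056 | 1.173 | 2.1% |

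Second row worked through: (1.00 + 1.21 + 1.3225 + 1.44)/4 = 1.243; √1.243 = 1.115; 1.115/1.2 = 0.929; 1.96 × 0.929 = 1.82; two-sided tail 6.9%.

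**3. All three structures, with dropout.** Each structure was fitted in large samples to a true covariance with AR(1)-type correlation (0.6 or 0.8 between adjacent visits) and 0% or 20% random dropout by Week 24. The model-based standard error was compared with the true one.

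| Assumed SDs | Ratio | Type I error |
|---|---|---|
| 1.2 throughout | 0.98 to 1.00 | 5.0% to 5.5% |
| 0.9/1.0/1.1/1.2 | 0.85 to 0.88 | 8.4% to 9.4% |
| 0.8/0.95/1.1/1.2 | 0.82 to 0.85 | 9.4% to 10.6% |
| 0.6/0.8/1.0/1.2 (steep) | 0.74 to 0.78 | 12.5% to 14.7% |
| Shrinking, 1.2 to 0.9 | 1.15 to 1.19 | 2.0% to 2.4% |

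The three structures barely differ: with 0.9/1.0/1.1/1.2 and complete data they give 8.4% to 8.5%. The 5.5% in the flat case is compound symmetry under 20% dropout, where it misfits the correlation rather than the variance.

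**4. Simulation check.** Over 10,000 null trials per scenario with 300 complete patients, compound symmetry gave 8.6%, 9.8% and 12.9% for the three growing patterns in step 3. Estimating the Week 24 variance separately gave 4.5% to 5.3% in all scenarios.

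**5. At the planned effect.** In the 10.1% scenario the reported standard error would be 1.005 × √(2/150) = 0.1161. The interval around 0.77 would be 0.54 to 1.00 instead of 0.50 to 1.04. Both exclude zero by a wide margin.

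**The case against.** The strongest reply is that the concern needs two things, and the documents make neither likely. First, the unstructured fit must fail. It has 4 × 5/2 = 10 covariance parameters and about 300 patients, so failure is improbable. Second, the Week 24 residual variance must differ from the average, and no variances by visit are given. Both points stand.

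A reader might infer that spread does grow over time, since Protocol 3.2 says HbA1c reflects roughly the previous 12 weeks, so Week 6 still carries pre-randomisation glycaemia. That makes growth plausible but does not establish it. The same fact suggests that most of any rise would come between Weeks 6 and 12, close to the nearly flat row of the table. Other features may limit late spread: HbA1c after rescue is set to missing (Protocol 7.4.1, SAP 6.6), and background therapy may be increased when FPG is high (Protocol 4.2.1). The model also adjusts for baseline HbA1c and its interaction with week, so what matters is residual variance, not the raw variance of change.

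A reader might also infer that this trial's type I error is 6% to 10%, or that any use of the fallback gives too narrow an interval. Neither follows. Those rates hold only within the fallback and only if spread grows.

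Sensitivity analyses by multiple imputation (SAP 6.6) and on the per-protocol and completer sets (SAP 6.3) are planned, and the text after SAP 7.4.1 is redacted. They may use another variance model, but they would not replace the primary result.

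**Conclusion.** The point holds as a conditional weakness in the fallback rule, and it is minor. If the unstructured model fails, every permitted alternative ties the Week 24 variance to the other visits, and nothing in the rule corrects a mismatch. Under the assumed growth patterns of step 2, type I error in that event is about 5.7% to 10.1%, and higher if growth is steeper. It is 5.0% to 5.5% if spread is flat, and about 2%, so conservative, if spread shrinks. These figures rest on assumed SDs before Week 24. Those in step 3 also rest on assumed correlations and dropout.

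At the planned difference, 5.56 standard errors, the conclusion would hardly change. What is exposed is the width of the confidence interval, and false-positive control if the true effect is small or absent.

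**What to change.** In SAP 7.4.1, and explicitly for FPG in SAP 7.5.2, replace or precede the fallback list with heterogeneous Toeplitz, heterogeneous AR(1) and heterogeneous compound symmetry, keeping Kenward-Roger. Selection by Akaike's criterion or a fixed order is acceptable; the problem is the candidate list, not the selection rule. If only an equal-variance structure converges, report the empirical (sandwich) standard error and state its degrees-of-freedom method, because Kenward-Roger adjusts the model-based covariance and does not carry over. A sandwich standard error does not remove bias that a wrong working covariance can cause under missing-at-random dropout, so it should be the last step.

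The cost is a sentence or two in the SAP and a few program options. Each heterogeneous structure has three more variance parameters than its equal-variance counterpart (7 against 4 for Toeplitz, 5 against 2 for the other two), so there is a slightly higher chance that a fallback also fails to converge. Estimand, data and sample size are unchanged.

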7.5 SECONDARY ENDPOINTS

7.5.1 Key Secondary Endpoint

Not Applicable.

7.5.2 Secondary endpoints

Proportion of patients with at least one hypoglycaemia accompanied by a glucose value during 24 weeks of treatment

Logistic regression for the proportion of patients experiencing at least one hypoglycaemia after 24 weeks will be performed on the FAS (OC); all on-treatment hypoglycaemias will be considered:

- up to drug stop date if a patient prematurely discontinues (Japanese patients that prematurely discontinue prior or at day 175)

- up to trial medication stop date – 1 if a non-Japanese patient does not prematurely discontinue
- up to day 175 if a Japanese patient does not prematurely discontinue prior day 176.

The model will include *treatment* as fixed effect and *baseline HbA_{1c}* and *baseline daily basal insulin dose* as linear covariates.

Frequencies regarding the number and percentage of patients experiencing at least one hypoglycaemia accompanied by a glucose value during 24 weeks in each treatment group will also be presented based on FAS(OC) .

Proportion of patients with HbA_{1c} on treatment <8.0% after 24 weeks of treatment

Logistic regression for the patients achieving HbA_{1c} <8.0% at Week 24 will be performed on FAS (NCF); patients who do not complete 24 weeks of treatment will be considered non-responders. The model will include *treatment* as fixed effect and *baseline HbA_{1c}* and *baseline daily basal insulin dose* as linear covariates. Patients with baseline HbA_{1c} <8.0% will be excluded from the analysis.

A frequency table with the number and percentage of patients with HbA_{1c} <8.0% at Week 24 in each treatment group will be also be presented based on FAS (NCF).

Proportion of patients with HbA_{1c} on treatment <7.0% after 24 weeks of treatment

Logistic regression for the patients achieving HbA_{1c} <7.0% at Week 24 will be performed on FAS (NCF); patients who do not complete 24 weeks of treatment will be considered non-responders. The model will include *treatment* as fixed effect and *baseline HbA_{1c}* and *baseline daily basal insulin dose* as linear covariates. Patients with baseline HbA_{1c} <7.0% will be excluded from the analysis.

Frequencies regarding the number and percentage of patients with HbA_{1c} <7.0% at Week 24 in each treatment group will be also be presented based on FAS (NCF).

Proportion of patients with HbA_{1c} lowering by at least 0.5% after 24 weeks of treatment

Logistic regression for the patients achieving lowering of HbA_{1c} by at least 0.5% from baseline at Week 24 will be performed on FAS (NCF); patients who do not complete 24 weeks of treatment will be considered non-responders. The model will include *treatment* as fixed effect and *baseline HbA_{1c}* and *baseline daily basal insulin dose* as linear covariates .

[figure not shown]
Frequencies regarding the number and percentage of patients with lowering of HbA_{1c} by at least 0.5% from baseline at Week 24 in each treatment group will be also be presented based on FAS (NCF).

[figure not shown]
Change from baseline in FPG after 24 weeks of treatment

[figure not shown]
Analysis of change from baseline in FPG will follow the strategy for the primary endpoint. MMRM will be used to analyse the mean changes from baseline in FPG after 24 weeks of treatments.

[figure not shown]
$$\begin{aligned} \text{FPG change from baseline} = & \text{overall mean} + \text{treatment} + \text{week} \\ & + \text{treatment by week interaction} \\ & + \text{baseline HbA}_{1c} + \text{baseline daily basal insulin dose} \\ & + \text{baseline FPG} \\ & + \text{baseline FPG by week interaction} \\ & + \text{random error.} \end{aligned}$$

[figure not shown]
The analysis will include the fixed, categorical effects of *treatment*, *week* and *treatment by week interaction*, as well as the continuous, fixed covariates of *baseline FPG*, *baseline daily basal insulin dose*, *baseline HbA_{1c}* and *baseline FPG by week*. An unstructured (co)variance structure will be used to model the within patient measurements. This analysis will be performed on FAS (OC).

[figure not shown]

